4.8.3 Immunogenicity Analysis

Immunogenicity results including anti-SYNT001 antibody, anti-SYNT001 neutralizing antibodies and anti-SYNT001 antibodies titer available at the time of the database lock will be summarized by cohort, visit and time point. Descriptive statistics will include mean, SD, CV, median, minimum, and maximum.

4.9 Analysis of Exploratory Endpoints

4.9.1 Exploratory Pharmacodynamic / Disease Activity Analysis

Exploratory PD and disease activity markers may include:

- D-dimer
- Antiphospholipid antibodies (lupus anticoagulant, anti-cardiolipin antibody, anti-beta-2-GP1 antibody)
- Antinuclear antibody titer
- Anti-dsDNA antibody titer
- Quantitative Coombs assay
- Cold agglutinins
- Fc gamma R2A receptor (FCGR2A)
- Complement component 3
- RNA sequencing
- Immunophenotyping including measurements of T cells, monocytes, natural killer (NK) cells, and B cells

All exploratory PD/disease activity data available at the time of the database lock will be summarized by cohort and visit. Descriptive statistics will include mean, SD, median, minimum, and maximum. Mean (\pm SD) of values and percentage change and absolute change from baseline will also be plotted.

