2.1.3 Exploratory Objectives and Endpoints

Exploratory Objectives	Exploratory Endpoints
To explore the effect of SYNT001 at different dose levels and dosing regimens on biomarkers to understand the pathophysiology of the disease and the SYNT001 mechanisms of action	
The exploration of SYNT001 mechanisms of action and effects of SYNT001 on pathophysiology summarized by dose, dosing regimen and time point, as determined by:
 
 • D-dimer • Antiphospholipid antibodies (lupus anticoagulant, anti-cardiolipin antibody, anti-beta-2-GP1 antibody) • Antinuclear antibody titer • Anti-dsDNA antibody titer • Quantitative Coombs assay • Cold agglutinins (titer and thermal amplitude) • Fc gamma R2A receptor (FCGR2A) single nucleotide polymorphisms (SNP) by genotyping • Complement component 3 levels by

Exploratory Objectives	Exploratory Endpoints
	nephelometry 
 • Presence of disease and inflammatory markers by total RNA sequencing • Immunophenotyping including measurements of T cells, monocytes, natural killer (NK) cells, and B cells by flow cytometry
To characterize blood transfusions during the study	The number of units of packed red blood cells received by subjects will be summarized by dose and dosing regimen
To determine the impact of different SYNT001 dose levels and dosing regimens on the subject's use of corticosteroids to treat their WAIHA	The evaluation of corticosteroid use during the study will be summarized by dose, dosing regimen and time point

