3. STUDY OVERVIEW

3.1 Overview of Study Design

This is a multicenter, open-label study to assess the safety, tolerability, efficacy, PK, PD, and immunogenicity of SYNT001 IV administered to subjects with WAIHA.

Up to 8 subjects with a diagnosis of WAIHA will receive SYNT001 10 mg/kg weekly x 5 doses (Cohort 1). Up to 12 subjects with a diagnosis of WAIHA will receive SYNT001 (10, 20 or 30 mg/kg) weekly x 3 doses (Loading), followed by SYNT001 (10, 20 or 30 mg/kg) every other week x 5 doses (Maintenance) or SYNT001 (10, 20 or 30 mg/kg) weekly x 10 doses (alternative weekly maintenance schedule) (Cohort 2). An overview of the study cohorts is provided in Table 1.

Table 1. Cohort Overview

Cohort	No. of subjects	SYNT001 Dose	No. of Doses	Frequency of Doses
1	Up to 8	10 mg/kg	5	Weekly
2	Up to 12	Loading: 10, 20 or 30 mg/kg Maintenance: 10, 20 or 30 mg/kg	3 5	Weekly Every other week
2 Alternative weekly schedule	Up to 12	Loading: 10, 20 or 30 mg/kg Maintenance: 10, 20 or 30 mg/kg	3 10	Weekly Weekly

Subjects in both cohorts will complete the following periods of assessment: Screening, Treatment, and Follow-Up. For Cohort 1 details of the dosing schedule and assessments, see Appendix [Table 2](#). For Cohort 2 details, see Appendix [Table 3](#). An alternative weekly maintenance schedule of assessment for Cohort 2 is presented in Appendix [Table 4](#).

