4.1 General Design

All clinical data captured will be provided in data listings. Subject disposition, demographic information, and baseline characteristics will be presented. Results will be summarized by dose and dosing regimen (cohort), and in total. Any discrepancy between treatment to be given and treatment received will be accounted for in these displays.

Continuous data will be described using descriptive statistics: number of observations (n), mean, standard deviation (SD), median, Q1 (25th percentile), Q3 (75th percentile), minimum, and maximum. Geometric mean (GM) and GM CV will be provided for PK parameters.

Categorical data will be summarized using frequencies and percentages. When categorical data are presented, the percent will be suppressed when the count is zero to draw attention to the non-zero counts. The denominator for all percentages, unless otherwise specified, will be the number of subjects in the specified analysis population.

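### Antinuclear, anti-dsDNA and cold agglutinin titers in SAP 4.9.1 would be better summarized on a log scale than by arithmetic mean, SD and mean percentage change

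*SAP*

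**What the plan says.** SAP 4.9.1 lists "Antinuclear antibody titer", "Anti-dsDNA antibody titer" and cold agglutinins among the exploratory markers. SAP 2.1.3 specifies cold agglutinins as a titer plus thermal amplitude. One rule covers the whole list, by cohort and visit: "Descriptive statistics will include mean, SD, median, minimum, and maximum". The mean (±SD) "of values and percentage change and absolute change from baseline will also be plotted". No log transformation, geometric mean or fold change is named for titers, and there is no rule for a result below the lowest dilution.

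Three other places bear on this:

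- SAP 4.1 confines its geometric-mean rule to PK: "Geometric mean (GM) and GM CV will be provided for PK parameters". SAP 4.8.1 extends it to PK concentrations.
- SAP 4.1 also provides, for continuous data in general, "median, Q1 (25th percentile), Q3 (75th percentile), minimum, and maximum".
- For the secondary markers, SAP 4.8.2 applies descriptive statistics to values, percentage change and absolute change. In 4.9.1, change appears only in the sentence about plots.

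SAP 3.1 sets the cohort sizes at up to 8 (Cohort 1) and up to 12 (Cohort 2).

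**The concern.** A titer read from serial dilutions moves in multiplicative steps. Two difficulties follow when it is summarized on the arithmetic scale, and they act on different summaries.

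The first is leverage. With 8 or 12 subjects, one reciprocal titer several dilutions above the rest can supply most of the arithmetic mean, and so most of the mean absolute change.

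The second is asymmetry. One two-fold step up is +100% and one step down is -50%, so reading error that is symmetric in dilutions does not cancel when individual percentage changes are averaged.

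Percentage change also has no defined denominator if the baseline result is below the lowest dilution. That can happen, because the eligibility criteria (protocol 5.2 and 5.3) do not require any of these titers to be positive.

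What is at stake is how readable an exploratory summary of mechanism markers is. No hypothesis test or success criterion depends on it.

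**Working it through.** The documents state no figure to reproduce: there is no sample size calculation, titer SD, dilution scheme or assay error. The cohort sizes come from SAP 3.1. The 59% fall is borrowed from protocol 2.2, where it is the reduction in total IgG in pemphigus subjects after the fifth dose. It serves only as an example and equals log2(1/0.41) = 1.29 two-fold dilutions. Titers and error sizes are assumptions, shown as ranges.

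**Leverage, n = 8.** Assume seven reciprocal titers of 40, 40, 80, 80, 80, 160, 160. They sum to 640, with mean 91 and geometric mean 80. Add one high subject:

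| High titer | Mean | Share of total | Geometric mean | Median |
|---|---|---|---|---|
| 160 | 100 | 20% | 87 | 80 |
| 640 | 160 | 50% | 104 | 80 |
| 1280 | 240 | 67% | 113 | 80 |
| 2560 | 400 | 80% | 123 | 80 |

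Take the last row and let titers fall four-fold in two ways:

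- Seven fall, the high subject does not. The sum goes from 3200 to 160 + 2560 = 2720, so the mean is 340 (-15%; mean absolute change -60). The geometric mean falls 70% and the median 75%.
- Only the high subject falls. The sum becomes 640 + 640 = 1280, so the mean is 160 (-60%; mean absolute change -240). The geometric mean falls 16% and the median does not move.

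The arithmetic mean thus understates a widespread fall and overstates an isolated one. With n = 12 and one subject at 2560, the mean is 297 (91 without that subject), a 72% share; the two scenarios give -21% and -54%. If the highest titer is 160, leverage is small (mean 100 against 91).

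**Mean percentage change.** Let each reading carry independent normal error with SD s, in doubling dilutions. The log2 ratio of follow-up to baseline then has error variance 2s², so

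E[follow-up/baseline] = true ratio × exp((s ln 2)²).

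For a true 59% fall and s = 1.0: 0.41 × 1.617 = 0.663, or -33.7%. The full range:

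| s | Factor | True -50% | True -59% | True -75% |
|---|---|---|---|---|
| 0.25 | 1.030 | -48.5% | -57.8% | -74.2% |
| 0.5 | 1.128 | -43.6% | -53.8% | -71.8% |
| 0.75 | 1.310 | -34.5% | -46.3% | -67.2% |
| 1.0 | 1.617 | -19.2% | -33.7% | -59.6% |

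A discrete version agrees. If each reading is off by one dilution with probability 0.25 each way, the factor is (0.25 × 2 + 0.5 + 0.25 × 0.5)² = 1.125² = 1.266. A true 59% fall then averages -48.1%, and no true change averages +26.6%. With probability 0.10 each way the factor is 1.1025, giving -54.8% and +10.3%.

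**Simulation.** In 40,000 trials at n = 8 and n = 12, for s = 0.5 to 1.0:

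- The shift does not shrink with n: at s = 1.0 the mean percentage change was -33.9% and -33.6%.
- Rounding to a two-fold grid moved it slightly further, to -31.3% and -30.8%.
- The geometric mean ratio returned -59% throughout.
- The median percentage change averaged between -53.7% and -58.3%.
- The ratio of arithmetic means, pooled over trials, also stayed at -59%, because the error inflates both expected means by the same factor.

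**The case against.** The strongest reply is that the quoted sentence already plans the median, minimum and maximum, that SAP 4.1 adds quartiles, and that SAP 4 lists all clinical data. In the leverage example the median stays at 80 whatever the high titer is, and the maximum reveals the high subject. This stands for values and removes most of the harm there. It does not extend to change from baseline, which 4.9.1 shows only as a mean (±SD).

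A reader might infer that the planned scale generally biases titers toward no fall. The calculations do not support that: the upward shift affects only the mean of individual percentage changes, and leverage can exaggerate a fall as readily as hide one.

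A reader might also infer that these titers are there to show whether autoantibodies fall with IgG, and that noise is as large as the expected effect. The documents do not say so. SAP 2.1.3 gives pathophysiology and mechanism of action as the purpose. The red-cell autoantibodies that the protocol treats as central are followed by the direct and quantitative Coombs tests. No fall is predicted for these three titers. The 59% is one of several IgG figures: protocol 2.2 also simulates a nadir reduction of about 78% for one regimen, which is log2(1/0.22) = 2.2 dilutions.

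Finally, the single rule cannot be meant literally for every item, since the list includes genotype and RNA sequencing. SAP 6 leaves mock tables to separate documents finalized before database lock, so a suitable titer display could still be specified there. But the SAP as written names a method for titers, and a better one is available.

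**Conclusion.** The point holds as a small improvement to an exploratory, descriptive summary. If titers are read in two-fold dilutions, a single high-titer subject can supply 50% to 80% of the mean in the n = 8 examples with a titer of 640 or more. Separately, a true 59% fall would average about -58% to -34% as a mean percentage change for an error SD of 0.25 to 1.0 dilution per reading. The upward direction of the second effect holds for any symmetric error above zero. The sizes of both effects depend on titers and assay error that the documents do not give, and leverage is minor if baseline titers are similar. The planned median, minimum and maximum already protect the summary of values. No primary or secondary conclusion is affected.

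**What to change.** In SAP 4.9.1, for the antinuclear antibody, anti-dsDNA and cold agglutinin titers only:

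- Keep median, minimum and maximum.
- Replace arithmetic mean and SD with the geometric mean titer.
- Report change from baseline as change in log2 titer, back-transformed to a geometric mean fold change, instead of percentage-change plots.
- Add the number of subjects with at least a four-fold (two-dilution) fall or rise.
- Assign results below the lowest dilution one fixed value, stated in advance.

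Leave the planned statistics in place for continuous markers such as D-dimer and C3. The anti-SYNT001 titer in SAP 4.8.3, also summarized by mean, SD and CV, could follow the same rule.

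The cost is SAP wording and one derived variable, with no new data. The geometric summaries will depend somewhat on the fixed value if many results fall below the lowest dilution, so the number of such results should be shown beside them.

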4.9.2 Blood Transfusions

The number of units of packed red blood cells received by subjects will be summarized by cohort.

4.9.3 Corticosteroid Use

The number and percent of subjects who use corticosteroid, and corticosteroid dose will be summarized by cohort and visit.

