Exploratory Objectives	Exploratory Endpoint
To explore the effect of SYNT001 at different dose levels and dosing regimens on biomarkers to understand the pathophysiology of the disease	The exploration of SYNT001 mechanisms of action and effects of SYNT001 on pathophysiology summarized by dose, dosing

and the SYNT001 mechanisms of action	regimen and time point, as determined by: 

• D-dimer

• Antiphospholipid antibodies (lupus anticoagulant, anti-cardiolipin antibody, anti-beta-2-GP1 antibody)

• Antinuclear antibody titer

• Anti-double-stranded deoxyribonucleic acid (dsDNA) antibody titer

• Quantitative Coombs assay

• Cold agglutinins (titer and thermal amplitude)

• Fc gamma R2A receptor (FCGR2A) single nucleotide polymorphisms (SNP) by genotyping

• Complement component 3 levels by nephelometry

• Presence of disease and inflammatory markers by total ribonucleic acid (RNA) sequencing

• Immunophenotyping including measurements of T cells, monocytes, natural killer (NK) cells, and B cells by flow cytometry

To characterize blood transfusions during the study	The number of units of packed red blood cells received by subjects will be summarized by dose and dosing regimen
To determine the impact of different SYNT001 dose levels and dosing regimens on the subject's use of corticosteroids to treat their WAIHA	The evaluation of corticosteroid use during the study will be summarized by dose, dosing regimen and time point

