#### **From screening until 2 weeks after the last dose of SYNT001**

The dose of corticosteroids taken for WAIHA or any other condition should remain stable ( $< 10\%$  change in dose level) from screening until 2 weeks after the last dose of SYNT001.

Corticosteroids should neither be started nor discontinued during this period with the exception of subjects who experience an IRR that requires corticosteroids as part of the management of the

IRR. Such subjects may receive corticosteroids prophylactically prior to subsequent SYNT001 infusions at the discretion of the Investigator.

From 2 weeks after the last dose of SYNT001 until end of study participation

At the discretion of the Investigator, but only after at least 2 weeks beyond the last dose of SYNT001, a slow corticosteroid taper may be started as per the following suggested schedule:

- If on >30 mg of prednisone per day, decrease by no more than 10 mg every two weeks until a final dose.

If per the Investigator's judgement, the subject would benefit from a change to the WAIHA treatment beyond the allowed steroid taper, this will be considered on a case-by-case basis in consultation with the Sponsor.

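### SAP 4.9.3 tabulates any corticosteroid by nominal visit, so it mixes in infusion-reaction steroids and, at Day 112, compares 70 with 14 days of permitted taper

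*SAP*

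**What the plan says.** **Objective.** SAP 2.1.3 states it as "To determine the impact of different SYNT001 dose levels and dosing regimens on the subject's use of corticosteroids to treat their WAIHA"; Protocol Section 3 has the same wording. The matching endpoint is broader: corticosteroid use during the study, by dose, regimen and time point.

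**Analysis.** SAP 4.9.3 is one sentence: "The number and percent of subjects who use corticosteroid, and corticosteroid dose will be summarized by cohort and visit". It gives no restriction on reason for use or route, no change from a reference dose, no dose conversion, and no time axis other than the visit.

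**Steroid rules.** In Protocol 6.10, the period headed "From screening until 2 weeks after the last dose of SYNT001" asks that any corticosteroid dose, for WAIHA or another condition, change by less than 10%. It adds: "Corticosteroids should neither be started nor discontinued during this period with the exception of subjects who experience an IRR that requires corticosteroids". After such a reaction, "Such subjects may receive corticosteroids prophylactically prior to subsequent SYNT001 infusions at the discretion of the Investigator". Only once two weeks have passed since the last infusion is there discretion to reduce: "a slow corticosteroid taper may be started as per the following suggested schedule".

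**Other routes to a start or increase.** The permitted-medications list in Protocol 6.10 allows treatment medically indicated for any adverse event. Protocol 8.5.3 foresees subjects who need a significant increase in WAIHA medication, who may then stop study drug but are encouraged to keep attending.

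**The concern.** Two features of the table work against the objective.

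First, the objective is limited to steroids "on the subject's use of corticosteroids to treat their WAIHA", but the table counts every user and every dose. During the stable-dose period the starts expressly allowed are for infusion reactions, and prophylaxis can then add the same subject at several later visits. A regimen with more infusion reactions would appear to use more steroid. That is a tolerability signal, not a WAIHA one. Protocol 9.6.2 names hydrocortisone as a possible treatment, while eligibility is expressed in prednisone or equivalent, so an unconverted dose summary can also mix drugs of different potency.

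Second, the cohorts finish dosing 56 days apart (Day 28 and Day 84). The same nominal visit therefore falls at different points relative to the date tapering becomes possible. A by-visit comparison of Cohort 1 with Cohort 2 then partly compares how long tapering had been allowed.

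**Working it through.** **Inputs**
- Last infusion: Cohort 1 Day 28 (Protocol 7.1.11); Cohort 2 Day 84 (Protocol 7.2.5; the weekly schedule in Protocol Table 10 also ends on Day 84).
- Last visit: Cohort 1 Day 112; Cohort 2 Day 140 (Protocol Tables 2 and 3).
- Stable-dose period ends 14 days after the last infusion (Protocol 6.10).

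**The plan's own figure first.** Protocol 4.4 gives follow-up of 84 and 56 days. Last visit minus last infusion: 112 − 28 = 84 and 140 − 84 = 56. Both reproduce. The documents state no taper length; it follows from these days.

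**When tapering may begin.** Last infusion + 14: Cohort 1, 28 + 14 = Day 42; Cohort 2, 84 + 14 = Day 98.

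**Visits under the restriction, counting all visits from Day 0**
- Cohort 1: Days 0, 1, 2, 5, 7, 12, 14, 19, 21, 28, 29, 30, 33 and 42 are on or before Day 42; Days 56, 84 and 112 are after. 14 of 17.
- Cohort 2, every other week: Days 0, 7, 14, 28, 42, 56, 70, 84 and 91 are before Day 98; Days 112 and 140 are after. 9 of 11.

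**Permitted taper days at shared visits** = max(0, visit day − day tapering may begin)

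| Nominal visit | Cohort 1 | Cohort 2 |
|---|---|---|
| Day 42 | 0 | 0 |
| Day 56 | 56 − 42 = 14 | 0 |
| Day 84 | 84 − 42 = 42 | 0 |
| Day 112 | 112 − 42 = 70 | 112 − 98 = 14 |

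Day 112 is the only shared visit with both cohorts past the restriction. Allowing for visit and dosing windows (last infusion Day 28 ± 6 hours or Day 84 ± 3 days; visit ± 5 days), the figures there are about 65 to 75 versus 6 to 22 days. By each cohort's last visit they are 70 and 140 − 98 = 42.

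**Aligned on days since last infusion**

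| Days since last infusion | Cohort 1 | Cohort 2 | Permitted taper days, each cohort |
|---|---|---|---|
| 28 | Day 56 | Day 112 | 28 − 14 = 14 |
| 56 | Day 84 | Day 140 | 56 − 14 = 42 |
| 84 | Day 112 | none | 84 − 14 = 70, Cohort 1 only |

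**Early stoppers.** A Cohort 2 subject whose last infusion was on Day 28 would have 112 − (28 + 14) = 70 permitted taper days at Day 112, against 14 for a completer in the same cohort. Alignment therefore has to use the actual last infusion.

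**The case against.** The strongest replies, and what stands of each:

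- **SAP 4.9.3 follows the endpoint as worded, and the restriction comes from the protocol.** This stands in part. No SAP wording can make the stable-dose period informative about steroid sparing. But the SAP can choose which steroids to count and on what time axis.
- **SAP 4.5 already summarises infusion-reaction medication, and table specifications are deferred to separate documents (SAP 6).** The SAP 4.5 summary does not remove those steroids from the 4.9.3 table. The deferred documents are not available here, and the SAP gives them no rule to apply. That infusion-reaction steroids would be counted is inferred from the missing filter; the SAP does not say so outright.
- **The harm is not quantified.** This stands. The documents give no rate of infusion-reaction steroid use in this study. In the pemphigus subjects described in Protocol 2.2, headache was the only drug-related event reported in more than one subject. Tapering is discretionary and the cohorts are not randomised.
- **Alignment does not restore the objective.** This stands. At 56 days after the last infusion subjects are off drug, and Protocol 2.2 reports IgG returning to baseline within one to two months in pemphigus.

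A reader might infer that steroid use can only rise before the restriction ends, or that infusion reactions are the only way in. The documents do not support this: changes under 10% in either direction are allowed, and the adverse-event permission and Protocol 8.5.3 leave other routes. A reader might also take 14 days as Cohort 2's whole taper window; it has 42 by Day 140.

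**Conclusion.** The mismatch is real but of low severity. The table does not isolate WAIHA steroids, and its visit axis confounds Cohort 1 versus Cohort 2 with taper opportunity: 70 versus 14 days at Day 112, and 70 versus 42 by end of study. In subjects who complete dosing this affects only that comparison, since both Cohort 2 schedules end on Day 84.

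It would go too far to say that Cohort 1 will show a lower dose at Day 112, or that the data can say nothing about steroid use. The first would require that tapering happens and that starting doses are similar. No dose difference in milligrams can be derived, because starting doses are not given and the suggested schedule states a step only for subjects above 30 mg of prednisone per day. As to the second, an off-drug description remains possible once indication and timing are handled.

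The day counts assume nominal visits and completed dosing. The endpoint is exploratory and descriptive, with no sample size calculation, so no formal conclusion of the study depends on it.

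**What to change.** Amend SAP 4.9.3 before database lock:

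1. Summarise systemic corticosteroids whose recorded reason for use is WAIHA, in prednisone equivalents with the conversion stated. Report infusion-reaction steroids separately.
2. Present post-treatment change from the dose at the end of the stable-dose period, by days since each subject's actual last infusion. Compare cohorts at 28 days (nominally Cohort 1 Day 56, Cohort 2 Day 112) and 56 days (nominally Cohort 1 Day 84, Cohort 2 Day 140). Keep Cohort 1 Day 112 as supportive. Cohort 2 has no visit at Day 98, so take the reference dose from the dated medication records.
3. Label visits within the stable-dose period as dose-restricted by protocol, but still report any increase in WAIHA steroids and any study-drug stop that follows from it.
4. State that the aligned result equalises taper opportunity and describes off-drug use, and does not by itself show steroid sparing.

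Separately, the corticosteroid rule and the adverse-event permission in Protocol 6.10, and Protocol 8.5.3, must be reconciled so that it is clear which starts and increases count as deviations.

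**Cost.** SAP wording and programming only. Protocol 6.10 already requires dose, route, dates and reason for use to be recorded; the fix assumes reason for use is also available for subjects enrolled before protocol amendment 5 (SAP 3.2.19). The downside is that Cohort 1 data beyond 56 days after the last infusion become supportive only.
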